12.0 Data Management

Limited demographic and personal health history data will be collected for the study. All screening data will be identified only by study number except for the consent form and a master enrollment file, which will be kept in a binder a the locked office, and password protected, respectively, per the requirements of the IRB.

All infants will be withdrawing from opioids, and will have had urine or meconium drug screens per clinical protocol. Also all fetal drug exposures will be a matter of clinical record, and not obtained for this study. We will not be doing any drug screening for this study. Study records will be kept confidential. However, as we will only have substance use information which is included in the clinical record and already known/reported to social services, we will not obtain a certificate of confidentiality.

Power Calculation: N/A. This is a convenience sample. We estimate we can enroll up to 20 patients within 12 months.

Statstical Analysis: tAN Finnegan scores obtained before and after will be compared within subjects by paired test.

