1.0 Objectives / Specific Aims

The overall aim of this proposed effort is to test transcutaneous auricular neurostimulation (tAN) as a therapeutic for opioid withdrawal and neonatal abstinence syndrome (NAS).

We hypothesize that tAN delivered for up to 60 minutes during peak withdrawal (1h before next morphine dose) will be safe, well tolerated and will decrease Finnegan withdrawal scores and shorten the length of morphine treatment compared with historical data.

Aim 1: Determine the safety and feasibility of auricular neurostimulation therapy in neonates with opioid withdrawal or NAS.

We hypothesize that auricular neurostimulation is safe and tolerable in both a single session, and 12-day treatment course. Furthermore, we believe target engagement can be validated by measuring stimulation-induced reductions in heart rate. Milestone: No adverse events of bradycardia (HR < 80 bpm), worsening of swallowing or feeding, skin irritation, or elevation of Neonatal Infant Pain Scores.

Aim 2: Demonstrate that auricular neurostimulation therapy in opioid withdrawing or NAS neonates reduces the Finnegan and/or WAT-1 scores from pre- to post-stimulation. We have used ear electrodes for taVNS in a similar stuy (#67997). However, in this prospective, open-label study we will use a novel, non-significant risk auricular neurostimulation device and ear electrodes to study 20 opioid withdrawing or NAS neonates at the Medical University of South Carolina. We aim to show a clinically-meaningful reduction in Finnegan scores, the routine assessment that includes 21 signs of withdrawal (Finnegan 1992). Alternatively, in infants who receive both opioids and benzodiazepine analgesics, we aim to show a clinically-meaningful reduction in Withdrawal Assessment Tool (WAT-1) scores, which is a validated, 11 item/12 point scale used to monitor opioid withdrawal in pediatric patients (Franck 2008). In the study, we will deliver up to 60 minutes of tAN 1 hour prior to each morphine administration, up to 4 times per day for up to 12 days. If morphine is weaned off at or before 10 days, a weaning phase for tAN will begin on the following day for 2 days: tAN Weaning Day 1: deliver tAN twice tAN Weaning Day 2: deliver tAN once We will assess each patient with standard Finnegan scores and/or WAT-1 before and after stimulation, and monitor use of morphine throughout the study. We expect a 25% reduction in Finnegan/WAT scores from before to after sessions of auricular neurostimulation.

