4.0 Study Endpoints

Safety Outcomes: 1) Skin irritation, assessed by staff daily. 2) NIPS pain scores recorded during treatment.

Efficacy Outcomes: 1) Finnegan scores before and after tAN will be recorded at each session or WAT-1 scores will be recorded with hands on care . 2) Duration of morphine weaning. 3) Length of stay We will also collect data on developmental outcomes from a short motor test in the nursery and from routine clinic visits to the NICU high-risk follow-up clinic up to 24months.

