6.0 Number of Subjects

Total Planned Enrollment: 20

Up to twenty neonates will be enrolled in this prospective, open-label safety and feasibility trial. The experimental paradigm consists of up to 60 minutes of tAN at the peak withdrawal time 1 hour before usual morphine dose every 3h, before feeding, up to 4 times per day, and up to 12 days or until morphine is weaned off. If morphine is weaned off at or before 10 days, a weaning phase for tAN will begin on the following day for 2 days:

- tAN Weaning Day 1: deliver tAN twice
- tAN Weaning Day 2: deliver tAN once

All consented participants will receive the active stimulation condition.

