10.0 Study Design / Methods

After obtaining consent and describing this procedure to the parents and all members of the baby's care team, we will first deliver stimulation per our protocol in #67997 to determine the perceptual threshold. We will use the identical method for determining the intensity for PT, which has proven to be safe as in our taVNS study in infant feeding. We will start with 0.2mA with a 250µs, 5Hz in vagus and 100Hz in trigeminal nerve area, and gradually increase the intensity of the TENS unit until the baby can first feel something in their ear. We will use the facial expression change, fidgety movements to determine when the infants feel the stimulation, as in the taVNS study. This intensity will be recorded as the **perceptual sensory threshold (PT)**. The procedure is detailed below.

Determination of Perceptual Threshold

- 1. Electrode clip will be placed on the left tragus in an enrolled infant at rest. Starting at 0.2mA at 5Hz in vagus and 100Hz in trigeminal nerve area, we will deliver 5 seconds of pulses, and increase by 0.1mA until the perceptual threshold is achieved by observation of the infant's facial expression, fidgety movements. This will be termed the perceptual threshold.
- 2. We will decrease the microcurrent by $\sim 0.1 \text{mA}$ below the perceptual threshold and administer this as the taVNS treatment dose 1h before the morphine dose and before the infant is feeding, every 3h, for 60 minutes, up to 4 times per day. Current will then be held constant while pulse width and frequency will be set at $250 \mu \text{s}$ and 5 Hz in vagus area and 100 Hz in trigeminal nerve area, respectively.
- 3. Finnegan scores will be rated before and immediately after the taVNS treatment, and per usual clinical protocol. WAT-1 scores will also be rated during tAN treatment per usual clinical protocol.
- 4. Physiological data will be monitored continuously as measured by the echocardiogram (ECG).
- 5. Neonatal Infant Pain Scale (NIPS) data collected at beginning and the end of treatment session. The NIPS rating scale currently in use in the nursery is included in this submission.

taVNS Protocol

These studies will be conducted in the Shawn [name] Children's Hospital's Neonatal Intensive Care Unit (NICU).

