Participants will receive tAN stimulation to their left ear via electrodes attached to the ear. The stimulation intensity we will use for tAN will be ~0.1mA less than PT or each infant. We will recalibrate the PT daily, and then deliver that current intensity for each session that day administered every 3h, starting 1h before the morphine dose. The current will be on for 5 minutes, off for 10 seconds, for up to 60 minutes total each session, up to 4 times per day, for up to 12 days or until morphine is weaned off. If morphine is weaned off at or before 10 days, a weaning phase for tAN will begin on the following day for 2 days. tAN Weaning Day 1: deliver tAN twice. tAN Weaning Day 2: deliver tAN once.

The nurses will score the NAS using the Finnegan scale before and after the treatment. The Withdrawal Assessment Tool (WAT-1) will also be used to assess infant withdrawal symptoms before and after treatment in infants receiving benzodiazepines and opioids (Franck 2008, 2013). The WAT-1 is an 11 item/12 point scale to monitor withdrawal and is routinely performed by nurses 3 times per 12 hour shift with hands on care.

Prior to beginning the study, Drs. [name] and [name] will perform an in-depth in service with the charge nurses of the neonatal nurseries, a limited pool of 10 nurses. They will also in-service the neonatal nurses at their staff meetings to introduce them to the study, the rationale, the protocol and the equipment. Most nurses are familiar with ear electrode stimulation from the taVNS-paired feeding study conducted over the past 18 months.

A short developmental test, the STEP, will be performed while the infant is stil in the nursery and at the first neonatal high-risk developmental clinic (outpatient) follow-up visit.

Safety Monitoring

Prior to determination of the daily sensory threshold of the infant by the study coordinator or research assistant, an initial pain level will be recorded using the NIPS. The nurse or other staff may decrease the current intensity or stop stimulation entirely if the infant shows signs of distress or an increase in NIPS score >3 above baseline. As opioid withdrawing infants frequently have higher NIPS, we will only halt or adjust stimulation if the NIPS is 3 greater than their baseline. The nursing staff routinely measure and record the NIPS throughout the day. We will monitor the relationship of increased NIPS scores to the up to 60 minute stimulation period daily.

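### Does the within-subject paired test of Finnegan scores wrongly treat an infant's repeated session pairs as independent?

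*Protocol*

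**What the plan says.** The statistical analysis in Section 12.0 is a single sentence: "tAN Finnegan scores obtained before and after will be compared within subjects by paired test". The type of paired test is not named, and neither is an alpha level. The same section reports no power calculation and calls the sample a convenience sample.

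The scores are collected session by session. Section 4.0 states: "Finnegan scores before and after tAN will be recorded at each session or WAT-1 scores will be recorded with hands on care". Section 10.0 has "Finnegan scores will be rated before and immediately after the taVNS treatment, and per usual clinical protocol" and, later, "The nurses will score the NAS using the Finnegan scale before and after the treatment". Sessions run "up to 4 times per day, and up to 12 days or until morphine is weaned off" (Section 6.0). Infants who stop morphine early have three further sessions, two on one day and one on the next: "If morphine is weaned off at or before 10 days, a weaning phase for tAN will begin on the following day for 2 days" (Section 10.0).

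Aim 2 in Section 1.0 gives an expectation, not a success criterion: "We expect a 25% reduction in Finnegan/WAT scores from before to after sessions of auricular neurostimulation". WAT-1 takes the place of the Finnegan score for some infants: "Alternatively, in infants who receive both opioids and benzodiazepine analgesics".

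**The concern.** A plain paired test needs one pair per independent unit. Here each infant may contribute dozens of pairs, and the 25% expectation is also worded in terms of sessions. An analyst could read the sentence as an instruction to enter every session pair as its own observation. If an infant's changes resemble one another, that overstates the information, so the confidence interval is too narrow and the p-value too small.

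Pooling would also give more weight to infants who wean slowly, and duration of morphine weaning is itself an efficacy outcome in Section 4.0. The Limitations paragraph of Section 10.0 concedes that an acute Finnegan difference may not appear, so a true null is plausible and false positives matter. The results are meant to inform a larger randomized trial, which an over-precise estimate could mislead.

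**Working it through.** The protocol has no power, alpha or precision figure to reproduce. The check asks what each reading of the sentence would do.

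**Inputs from the protocol.** 20 infants; up to 4 sessions per day; up to 12 days; 2 + 1 = 3 extra sessions if morphine stops by day 10.

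**Assumptions.** Two-sided 5% test; intraclass correlation (ICC) of the session change scores from 0 to 0.10; weaning on day 5 as an example of a short course. The protocol gives none of these.

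**Maximum pairs per infant (m).**
- Weaned on day 5: 4 × 5 + 3 = 23
- Weaned on day 10: 4 × 10 + 3 = 43
- Not weaned by day 12: 4 × 12 = 48, or 48 × 20 = 960 pairs if all infants do this

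Under pooling, the relative weights are 48/23 = 2.1 and 48/43 = 1.1.

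**False-positive rate if all pairs are pooled.** Design effect DE = 1 + (m − 1) × ICC; rate = 2 × (1 − Φ(1.96/√DE)).

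| ICC | DE, m = 23 | Rate | DE, m = 48 | Rate |
|---|---|---|---|---|
| 0 | 1.00 | 5.0% | 1.00 | 5.0% |
| 0.01 | 1.22 | 7.6% | 1.47 | 10.6% |
| 0.05 | 2.10 | 17.6% | 3.35 | 28.4% |
| 0.10 | 3.20 | 27.3% | 5.70 | 41.2% |

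Simulation with 20 infants and no true effect (10,000 runs per setting) agrees within about one percentage point. With weaning spread evenly over days 5 to 12, the simulated rates are 5.1%, 9.1%, 24.7% and 37.3%. With 10 or 15 infants they are almost the same, so moving some infants to WAT-1 makes no difference to this calculation.

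**False-positive rate with one mean change per infant.** Simulated rates lie between 4.6% and 5.5% in every setting.

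**Interval width, 20 infants, in session-SD units.** The pooled half-width is t(20m − 1)/√(20m). The infant-level half-width is t(19) × √((ICC + (1 − ICC)/m)/20).
- m = 48, ICC 0.10: 0.161 against 0.063, ratio 2.55
- m = 23, ICC 0.10: 0.175 against 0.092, ratio 1.91
- ICC 0: ratio 1.07 for either m

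**Which reading does the text support?** Section 12.0 places the comparison within subjects. Sections 4.0 and 10.0 say when scores are recorded, which is a matter of data collection and does not set the unit of analysis. No section says that session pairs are to be treated as independent. The rates in the table therefore describe a possible misuse of the sentence, and the infant-level results describe a reading that its words allow.

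**The case for a change.** The best case for a change is that the protocol does state an analysis here, so this is more than silence. The one named efficacy test is of a kind that takes one pair per unit, while the data arrive as many pairs per unit. A phrase about comparison within subjects could equally describe pairing before with after inside a session. An analysis plan written from this sentence would inherit the ambiguity, and a line naming the infant as the unit would cost nothing.

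Part of this stands. The sentence is brief, the arithmetic is correct under its assumptions, and with this many sessions even an ICC of 0.01 would roughly double the error rate at m = 48.

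It does not show an error, however. The sentence is correct on a natural reading, and the test type is left open, so a mixed model or infant means would both be consistent with its intent. Unequal weighting is not wrong in itself either: a session-weighted mean is a legitimate target and fits the way Aim 2 words its expectation. A prescribed fix would also bring choices of its own, such as whether sessions after morphine has stopped belong in the average, and how to pair WAT-1 scores that Section 4.0 ties to hands-on care. Those choices belong in an analysis plan.

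**Conclusion.** No change to the plan is needed. The gap is real but ordinary: reducing repeated pairs to one comparison is commonly left to the analysis plan, which was not available for this review, and a competent analyst would use infant means or a model with a random infant effect.

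The possible harm, a false-positive rate of about 27% to 41% at an assumed ICC of 0.10, depends on pooling that the protocol does not state and on a correlation that it does not give. At ICC 0 there is no inflation. No stated figure or rule would be corrected, because the study has no alpha, power or efficacy decision rule. All infants receive active stimulation, so no p-value from this comparison can attribute a change to the device, however it is computed. Naming the infant as the unit when the analysis is written up would be a courtesy to the reader and would correct nothing in the protocol.

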13.0 Provisions to Monitor the Data to Ensure the Safety of Subjects

Drs. [name] and [name] will ensure confidentiality of the subject data, monitor and review adverse events, and minimize possible risks associated with tAN procedures.

Regarding informed consent, participants are fully advised on the research procedures to be used, the amount of time required of them, the possible risks and benefits of the procedures, their right to refuse participation in the study without prejudice, their right to terminate participation at any moment without prejudice, and the name and telephone number of the principal investigator. All subjects will be required to have capacity to consent.

Regarding confidentiality, subjects are informed that the information they provide will be kept strictly confidential, with access limited to the research staff. Participation in the study will be treated as confidential, as will all records. The identity of subjects will be protected with alphanumeric codes. All data will be kept in locked file cabinets or in password-protected files on secure servers with access by study team members only.

Spark biomedical personnel will receive de-identified patient data via our clinical trial agreement under the SBIR. Spark biomedical personnel may review identified patient data on site visits.

We do not anticipate any adverse events to occur in this study, however the experienced research team has a long standing record of recording and reporting unanticipated adverse events to the IRB.

14. Withdrawal of Subjects

If any parent wishes to withdraw their infant from treatment, we will immediately terminate the tAN sessions, but still continue to collect information on the morphine dosing and length of stay. If a parent wishes to withdraw from the study entirely, then no further data will be collected on the patient, but safety and treatment data up to that point will be retained under deidentified study number.

15.0 Risks to Subjects

tAN is another form of taVNS using transcutaneous electrical nerve stimulation (TENS) of the auricular branches of the vagus and trigeminal nerves that innervate the ear. Although this novel therapeutic modality is still in the development and optimization process, risks are a combination of those to be expected by both the peripheral TENS and taVNS, which has been safely used in neonates and infants at MUSC by the study team: Heart rate decrease, discomfort and skin irritation.

Theoretical risks associated with neuromodulation of the parasympathetic nervous system via taVNS would also be applicable in the administration of noninvasive tNS, including reduction of heart rate. In the taVNS study we observe a transient 10% decrease of baseline HR with onset of stimulation and rapid rebound within 60 seconds. We have seen no epsidsodes of bradycardia related to taVNS stimulation and expect none in this protocol.

TENS devices are FDA approved for pain relief and are available over the counter. The main risks associated with TENS is that stimulation may result in discomfort. The unit used in this studies is an FDA 510(k) cleared electrical stimulator that meets the rigorous electrical standards of the FDA. Skin irritation, redness, or inflammation may occur under the stimulating electrodes if TENS current is delivered for a prolonged period of time, but is not expected with up to 60 minutes of stimulation, similar to the duration of taVNS in protocol #67997.

Given the minimal risk both of these already FDA approved methods, we expect tAN like taVNS, will be a very safe procedure.

Risk of loss of confidentiality: We will assign study numbers to each participant, keep CRF and consent forms in locked cabinets in locked offices. Database files with names and contact information will be password protected and stored on the MUSC Pediatric server. All other data files related to this study will be identified by participant number only, without link to standard identifiers. We will publish the aggregate data only.

Unknown Risks: TENS stimulation of peripheral nerves is FDA approved and is considered very safe. Although tAN is essentially TENS on the ear, it is still an experimental procedure that has not been approved by the FDA to improve outcome of infants with opioid withdrawa symptoms. Therefore, there may be risks and discomforts that we are not aware of.

16.0 Potential Benefits to Subjects or Others

tAN delivered at the peak time of withdrawal between doses of morphine may decrease behavioral scores on the Finnegan scale, and enable faster weaning of morphine or adjunctive medications and possibly earlier discharge from hospital. The treatment could potentially help avoid escalation

of morphine doses. tAN may also decrease scores on the WAT-1 scale. However, there may be no direct benefit to the participant, but we will gain knowledge about tAN in infants, and this information may help develop strategies to improve treatment of opioid withdrawal and NAS.

17. Sharing of results with subjects: Individual study results will be known to parents and care providers, as this is an open label study. Overall study results will not be shared with subjects unless they request it.

